### **Primary and secondary objectives**

The primary end point of our study is the comparison in platelet reactivity measured by VerifyNow PRU between crushed ticagrelor LD plus cangrelor infusion and crushed ticagrelor LD (plus placebo infusion) at 30 min after the LD and cangrelor (or placebo) bolus. We hypothesize that adding cangrelor will significantly reduce PRU in patients with STEMI undergoing PPCI. Secondary objectives will include: 1) the comparison in PRU between cangrelor and placebo at the other time points; 2) the comparison in PRI at all time points; 3) the comparison in rates of HPR between cangrelor and placebo at all time points. According to consensus definition, HPR will be defined as PRU>208 or PRI>50% [19].

### **Sample Size Computation, Power Analysis and Statistical Analysis**

Assuming a common standard deviation of 70 PRU, a sample size of 20 patients per group will allow to detect a 70 PRU difference between groups (~160 PRU with ticagrelor vs ~90 PRU with ticagrelor plus cangrelor) with 85% power and a two-sided  $\alpha = 0.05$ . Considering the 2 arms and a possible ~25% rate of invalid results due to hemolysis, technical problems, or drop-out, we plan to randomize up to 50 patients, in order to have complete data for the primary

end point analysis. Our sample size is based on data derived from previously published studies [10,20,21].

The PD population will include all patients with PD data and without a major protocol deviation thought to affect significantly the PD of ticagrelor or cangrelor. The PD population will be used for analysis of all primary and secondary PD variables. Erroneously treated patients (e.g., those randomized to one treatment but actually given the other) will be accounted for based on the actual treatment received.

Categorical variables will be expressed as frequencies and percentages. Continuous variables will be presented as mean  $\pm$  SD or median [IQR]. Continuous variables will be analyzed for normal distribution with the Kolmogorov-Smirnov test. Comparisons between categorical variables will be performed using two-tailed Fisher's exact test or the Pearson's chi-square test. Student's t test, Mann-Whitney U-test and Wilcoxon test will be used to compare continuous variables when appropriate. An analysis of covariance will be used to evaluate the primary end point and all between-group comparisons in platelet reactivity. A mixed linear model will be used to evaluate the overall difference between groups over time and within-group comparisons. A p value  $<0.05$  will be considered statistically significant for superiority analyses. Statistical analysis will be performed using a SPSSv22.0 software (SPSS Inc. Chicago, IL).

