### **Publication Strategy/Additional Information**

Subjects will be identified with a number and data collection sheets will all be stored in a locked area. Data will be kept for 6 years after enrollment ends to comply with HIPAA regulations. Patients will receive a handout with the names and telephone numbers of the doctors involved in the study. Study subjects will be identified first (months 1-12): we expect to

randomize 4-5 subjects monthly and complete enrollment in 12 months (total: 50 subjects randomized). Months 13-14 will be implied for statistical analysis and manuscript preparation. Results will be presented at the first available major cardiovascular meeting (e.g. AHA, ACC, ESC), and final manuscript will be submitted to publication to one of major cardiovascular journals (e.g. JACC, Circulation, European Heart Journal).

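### Randomising 50 patients covers a 20% loss, not the stated 25% or so, if 20 per group are to be evaluable; the effect on power is small

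*Combined protocol and SAP*

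**What the plan says.** The section on sample size, power and statistical analysis (combined protocol and SAP) gives three linked figures.

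- **Evaluable patients needed.** It states that "a sample size of 20 patients per group will allow to detect a 70 PRU difference between groups", "with 85% power and a two-sided" alpha of 0.05. The common standard deviation is taken as 70 PRU. With two arms this means 40 evaluable patients.
- **Loss and number randomised.** It allows for "a possible ~25% rate of invalid results due to hemolysis, technical problems, or drop-out, we plan to randomize up to 50 patients". The stated purpose is complete data for the primary end point analysis.
- **Analysis.** "An analysis of covariance will be used to evaluate the primary end point and all between-group comparisons in platelet reactivity". No covariate is named, and no correlation with the outcome is given.

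Allocation is 1:1 (Research Design). The total is repeated under Publication Strategy/Additional Information, where the plan is to "complete enrollment in 12 months (total: 50 subjects randomized".

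**The concern.** A loss allowance tells the reader how many randomised patients can fail to give a usable primary result before the trial falls below its planned size. Here a reader would conclude that the trial can lose a quarter of its patients and still analyse 20 per group. It cannot, because a quarter of 50 is more than the 10 patients that separate 50 from 40.

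The number randomised is worded as a ceiling, and the document makes no provision for replacing patients. It does provide for removing them: those given glycoprotein IIb/IIIa inhibitors before the primary time point are excluded, and those with a major deviation affecting the pharmacodynamics are left out of the PD population. At the loss the plan itself anticipates, it would therefore usually miss its own target. What is at stake is the accuracy of a stated design figure and, to a small degree, power.

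**Working it through.** **Inputs.** All come from the sample-size section except the allocation, which is under Research Design: difference 70 PRU; common SD 70 PRU; two-sided alpha 0.05; 20 evaluable per group; loss about 25%; at most 50 randomised; allocation 1:1.

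**Step 1. Reproduce the base figure.** The standardised difference is 70/70 = 1. For a two-sample t test with n1 and n2 patients, the noncentrality is 1/√(1/n1 + 1/n2) on n1 + n2 − 2 degrees of freedom. With 20 per group this is √10 = 3.16 on 38 degrees of freedom, and power is 86.9%. The stated 85% is reproduced to within 2 points. The smallest equal group size reaching 85% is 19.

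**Step 2. Apply the stated loss.**

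- Evaluable at 25% loss: 50 × (1 − 0.25) = 37.5, against 40 planned.
- Largest loss that leaves 40 of 50: 1 − 40/50 = 20%.
- Number randomised that would leave 40 at 25% loss: 40/0.75 = 53.3, so 54.
- Likely origin of the 50: 40 × 1.25 = 50, which adds 25% of the evaluable number instead of dividing by the proportion retained.

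**Step 3. Effect on power** (unadjusted t test, SD 70 PRU).

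| Evaluable per group | Total | Loss from 50 | Power at 70 PRU | Difference detectable with 85% power |
|---|---|---|---|---|
| 20 / 20 | 40 | 20% | 86.9% | 68.1 PRU |
| 19 / 19 | 38 | 24% | 85.1% | 69.9 PRU |
| 19 / 18 | 37 | 26% | 84.0% | 71.0 PRU |
| 18 / 18 | 36 | 28% | 83.0% | not calculated |

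A loss of exactly 25% falls between the second and third rows. If each patient is lost independently with probability 0.25, starting from 25 per arm (independence is an assumption), average power is 84.0%.

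**Step 4. Chance of reaching the target.** Under the same assumption, the probability of at least 40 evaluable out of 50 is about 26%. The probability of at least 20 in both arms of 25 is about 14%.

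**Step 5. Allow for analysis of covariance.** The document gives no correlation, so I assume one covariate with outcome correlation r, take the residual SD as 70 × √(1 − r²), and deduct one degree of freedom. Power with 19 and 18 patients is then 84.0% at r = 0, 85.4% at r = 0.2, 87.2% at r = 0.3 and 89.7% at r = 0.4.

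**The case against.** The best defence is that the plan promises power, and power is almost untouched. Because 20 per group is slightly more than 85% power requires, 38 evaluable patients (19 per group, a 24% loss) still give 85.1%. The allowance is written as possible and approximate, and 24% is within rounding of it. The primary analysis is an analysis of covariance and a baseline sample is taken, so adjustment could recover the remaining point or so.

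This stands as an argument about weight, and it is why the point is minor. It does not make the stated figures agree. The section sets its target as 20 per group, and that count fails for any loss above 20%; even 22% leaves 39. The gain from adjustment is plausible, but it rests on a correlation that the document does not give.

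One could also read the 25% as an addition to the 40, which reproduces the 50 exactly. That explains the figure but does not rescue it. The text speaks of a rate of invalid results or drop-out, and those events happen to randomised patients. Ten lost out of 50 is a rate of 20%.

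**Conclusion.** The point holds, as a low-severity correction of a stated figure. Fifty randomised patients yield the planned 40 only if the loss is at most 20%. At the stated 25% the expected number evaluable is 37.5, a shortfall of 2 to 3 patients.

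Power at that loss is about 84% by an unadjusted t test, against 85% stated and 86.9% with the full 20 per group. This rests on the plan's own difference and SD. Analysis of covariance may bring power at 19 and 18 back to 85% or above (84.0% to 89.7% for an assumed correlation of 0 to 0.4). Neither the validity of the primary comparison nor the likely conclusion of the trial is in question.

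**What to change.** Change one sentence in the sample-size section, in either of two ways:

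1. State that randomising 50 patients allows for about 20% invalid results or drop-out while leaving 20 evaluable per group.
2. Keep the 25% and state that about 37 to 38 patients (18 to 19 per group) would then be evaluable, giving about 84% power by an unadjusted two-sample t test.

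Neither adds patients or changes conduct or analysis. The cost is that the stated allowance falls from 25% to 20%, or that power after loss is shown as about 84%. Raising the number randomised to 54 would also make the figures agree, but I would not ask for it: it recruits four more patients to gain about 3 points of power (86.9% at 20 per group against about 84%) when the 85% target is already nearly met.

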### **Publication Strategy/Additional Information**

Subjects will be identified with a number and data collection sheets will all be stored in a locked area. Data will be kept for 6 years after enrollment ends to comply with HIPAA regulations. Patients will receive a handout with the names and telephone numbers of the doctors involved in the study. Study subjects will be identified first (months 1-12): we expect to

randomize 4-5 subjects monthly and complete enrollment in 12 months (total: 50 subjects randomized). Months 13-14 will be implied for statistical analysis and manuscript preparation. Results will be presented at the first available major cardiovascular meeting (e.g. AHA, ACC, ESC), and final manuscript will be submitted to publication to one of major cardiovascular journals (e.g. JACC, Circulation, European Heart Journal).

### **Possible Discomforts and Risk**

In clinical trials, the most common clinical side effect of cangrelor was bleeding. Severe/moderate bleeding occurred in 0.8% of patients receiving cangrelor, as compared to 0.6% of those receiving placebo. Other side effects include dyspnea (1.3%), worsening renal function (3.2% of patients with severe renal impairment), and hypersensitivity (0.05%) [11,12].

All clinical events described above, if they were to occur, as well as death, myocardial infarction, stroke, and urgent revascularization procedure with PCI or coronary artery bypass grafting will be recorded. Bleeding data will be collected using BARC definitions [22]. Clinical events will be evaluated by a local committee, comprised of 2 faculty members (2 cardiologists), not directly involved in the research. In the event of a report of a serious adverse event the local committee will meet and antiplatelet treatment management will be managed according to physician recommendation.

### **Definition of Adverse Events**

An adverse event is any unintended or undesirable experience that occurs during the course of the clinical investigation whether or not it is considered to be therapy related. This includes any newly occurring event or previous condition that has increased in severity or

frequency since the initiation of study treatment. Adverse events will be followed until resolution while the patient remains on-study. Once the patient is removed from study, events thought to be related to the study therapy will be followed until resolution or until the patient starts a new treatment regimen.

**Serious Adverse Events (SAE):** An adverse event occurring while on study and considered related (reasonable possibility that the study treatment caused the adverse experience) to the study treatment that results in any of the following outcomes:

- Death
- A life-threatening adverse experience.
- A persistent or significant disability, incapacity, or is a congenital anomaly, or birth defect.
- Requires inpatient hospitalization, or prolongation of existing hospitalization.

The definition of serious adverse event also includes 'important medical event'. Medical and scientific judgment should be exercised in deciding whether expedited reporting is appropriate in other situations, such as important medical events that may not be immediately life-threatening or result in death or hospitalization but may jeopardize the patient and/or may require medical or surgical intervention to prevent one of the other outcomes listed in the definition above. These should also usually be considered serious. Examples of such events are intensive treatment in an emergency room or at home for allergic bronchospasm; blood dyscrasias or convulsions that do not result in hospitalization; or development of drug dependency or drug abuse.

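### The serious adverse event definition requires relatedness, so a death or other serious outcome judged unrelated is not an SAE and does not trigger the committee meeting

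*Combined protocol and SAP*

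**What the plan says.** In Definition of Adverse Events, an adverse event counts "whether or not it is considered to be therapy related". The SAE definition in the same section is narrower: "An adverse event occurring while on study and considered related (reasonable possibility that the study treatment caused the adverse experience"), and it must also result in death, a life-threatening experience, disability or congenital anomaly, or hospitalization or its prolongation. A further paragraph adds important medical events and calls for judgement in "deciding whether expedited reporting is appropriate in other situations".

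On follow-up, the section states: "Adverse events will be followed until resolution while the patient remains on-study". After that the scope shrinks: "Once the patient is removed from study, events thought to be related to the study therapy will be followed until resolution", or until a new treatment regimen begins.

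Possible Discomforts and Risk contains the oversight step: "In the event of a report of a serious adverse event the local committee will meet". It also requires that "All clinical events described above, if they were to occur", be recorded together with death, myocardial infarction, stroke and urgent revascularization, and that bleeding be collected by BARC definitions. It adds: "Clinical events will be evaluated by a local committee". That committee is two cardiologists not directly involved in the research.

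**The concern.** Seriousness and causality are separate attributes of an event, and the SAE definition merges them. Someone must judge an event related before it can be serious, and only a serious event triggers the meeting. A causality call therefore comes before an independent look at the event. The documents do not say who makes that call.

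The trial is double-blind, so known allocation should not steer the judgement. Blinding also leaves the attribution of any single event uncertain. In patients presenting with STEMI, the underlying disease is a ready alternative explanation for many serious events. Attribution is thus a weak gate for an oversight step. At stake is safety oversight only; the primary and secondary pharmacodynamic comparisons do not use SAE status.

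**Working it through.** No rate, power or sample size enters this point. The check sets the provisions side by side and counts what each one covers.

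1. **SAE status of an event judged unrelated.** The definition has the form: SAE = related AND (outcome 1 OR 2 OR 3 OR 4). The outcomes are death; life-threatening; disability, incapacity, congenital anomaly or birth defect; and hospitalization or its prolongation. If related is false, the expression is false whatever the outcome. An unrelated event qualifies under 0 of 4.

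2. **The important medical event paragraph.** It does not repeat the relatedness condition, but it addresses situations other than the listed outcomes, namely events that may not be immediately life-threatening or lead to death or hospitalization. It does not bring the four outcomes back in. If its silence means that relatedness is not needed there, a lesser unrelated event could be an SAE while an unrelated death could not.

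3. **The meeting trigger.** The only stated trigger is a report of an SAE. From step 1, an unrelated event with a listed outcome does not produce one.

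4. **What is recorded regardless of relatedness.** Possible Discomforts and Risk names bleeding, dyspnea, worsening renal function and hypersensitivity (4), plus death, myocardial infarction, stroke and urgent revascularization (4): 4 + 4 = 8 event types, with no causality condition.

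5. **Overlap of that list with the four outcomes.** Death is on the list in its own right: 1 of 4. The other 4 − 1 = 3 outcomes are covered only when the event is one of the other 8 − 1 = 7 named types, or when clinical events is read to mean all clinical events. Outcomes and diagnoses are different kinds of category (a stroke may be life-threatening and also disabling), so this count describes what is named. It is not a proportion of events missed.

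6. **Routes to the committee for an event judged unrelated.**

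| Event | Recorded | Evaluated by committee | Triggers meeting |
|---|---|---|---|
| One of the 8 named types | Yes | Yes, no timing stated | No |
| Serious, off the list, narrow reading of clinical events | As an adverse event | No stated route | No |
| Serious, off the list, broad reading | As an adverse event | Yes, no timing stated | No |

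7. **Follow-up.** Unrelated events are followed while the patient is on study, and the documents give no end to that period. For scale only, Research Design sets a 2 h infusion and a last infusion-timed sample 2 h after it stops: 2 + 2 = 4 h after the bolus. After removal from study, only events thought related are followed.

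**The case against.** The best reply is that little is lost in practice. Death and the other named events are recorded and evaluated by the same two independent cardiologists whatever their cause. The meeting has no stated timing or power beyond that evaluation, such as unblinding or a stopping rule. The relatedness threshold is only a reasonable possibility, so doubt should push events into the SAE category. Both arms also receive ticagrelor, so if study treatment includes it, a drug relation is hard to exclude even on placebo. A broad adverse event definition with a narrower serious subset is not a contradiction. Removing the condition could also make many prolonged index stays SAEs.

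Much of this stands. It would be wrong to say that unrelated deaths go unrecorded or unreviewed. The low threshold narrows the gap, the definitions are a design choice and not an internal conflict, and the extra burden is real. It does not close the gap. No listed outcome judged unrelated triggers the meeting, and a serious event off the list reaches the committee only on a broad reading of an undefined phrase. A low threshold still has to be applied by someone, and no one is named.

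**Conclusion.** The concern holds on the plain text. An on-study death, life-threatening event, disability or hospitalization judged unrelated is not an SAE and triggers no committee meeting. The effect is limited to safety oversight and is partly offset by the cause-blind recording of eight event types and the committee's evaluation of clinical events. The gap is clearest for serious events outside that list.

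The conclusion rests on reading the relatedness phrase as a condition on all four outcomes, which is how the sentence is built, and on the SAE report being the only meeting trigger, since no other is stated. How many events would be affected cannot be estimated, because the documents give no rate for serious events judged unrelated. This should be changed because the rule itself sorts serious events by a causality opinion, and correcting it is cheap.

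**What to change.** Remove the relatedness condition from the SAE definition, so that it covers any adverse event on study that leads to one of the listed outcomes. Record relatedness as a separate data field, completed by a named assessor role. Leave the meeting trigger in Possible Discomforts and Risk as it is; it would then apply to every SAE so defined.

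The cost is a one-sentence amendment, one data field and one named role, plus some additional SAE reports and meetings of the existing two-member committee, mainly for prolongation of the index stay judged unrelated. The documents give no figure from which to estimate how many. Sample size and the pharmacodynamic analysis do not change.

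A lighter alternative is to state that clinical events includes all serious events regardless of cause. That would secure evaluation for events off the list, but would still leave them, and unrelated deaths, without a meeting trigger. Neither change alters the end of the on-study period or the follow-up of unrelated events after removal from study; the same amendment could clarify both.

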### **Conflict of Interest**

[name] is a consultant for Chiesi, the maker of cangrelor, and Astra Zeneca, the maker of ticagrelor.

